12.2. LABORATORY EVALUATIONS

Observed and change from baseline clinical laboratory data (hematology, biochemistry and continuous urinalysis parameters) will be summarized by visit using descriptive statistics.

Observed, change from baseline and percent change from baseline values for BSAP, parathyroid hormone, vitamin D and urine NTx will be summarized by visit using descriptive statistics. The summary will also be split by sex and baseline menopausal status (i.e., men, pre-menopausal women and post-menopausal women). For NTx only subjects who have a second void collected at the visit will be included in the summary presentations (including the plots specified below).

Urinalysis categorical data will also be summarized by visit. Descriptive statistics will be used for continuous data and counts and percentages for categorical data.

A shift table from baseline to visit, of normal, abnormal low, abnormal high and missing records will also be summarised for hematology, chemistry and urinalysis data, with marginal totals, using counts and percentages. If the reference range does not have a lower bound (e.g., reference range is 0 to x), the low columns/rows will be presented as ‘-’, rather than a count of zero.

Box plots of changes from baseline by visit and group will be presented for the clinical laboratory parameters hemoglobin, HbA1c, high density lipoprotein (HDL), low density

lipoprotein (LDL), lymphocytes, leukocytes, platelets, neutrophils, vitamin D, calcium, CK, ALT, AST, BSAP and urine N-terminal telopeptide (NTx) values. The whiskers will display the 5th and 95th percentiles. For the reporting group from the start of REN001-202 the box plot will be repeated for the overall mt-DNA-PMM versus nDNA-PMM groups and outliers (i.e., outside the 5th to 95th percentile) will be identified on the plot with subject ID. The number of observations contributing to each visit will be included on the plot. The box plot will be repeated for the parameters BSAP and urine N-terminal telopeptide (NTx) however these plots will be presented by sex and baseline menopausal status (i.e., men, pre-menopausal women and post-menopausal women).

Subjects who satisfy the criteria for values of potential clinical importance (PCI), identified in the table below, will be summarized and listed. The summary will present the number of subjects with at least one on-treatment post baseline value (including unscheduled visits) satisfying the criteria. The listing will have a similar layout to the overall laboratory listing but will only include those subjects who satisfy the criteria for a specific parameter. The records satisfying the criteria will be identified on the listing. The criteria are:

Category	Parameter	Criteria
Chemistry	Creatine kinase (CK)	Normal baseline value and post $\geq 5 \times$ ULN > ULN baseline value and post $\geq 5 \times$ baseline level
	Aldolase	Normal baseline value and post > ULN
	Troponin I	> ULN
	Potential Hy's Law (ALT, AST, total bilirubin and alkaline phosphatase)	ALT or AST > 3 x ULN and Total bilirubin > 2 x ULN and Alkaline Phosphatase $\leq 2 \times$ ULN

An evaluation of Drug-Induced Serious Hepatotoxicity (eDISH) plot will be generated. The plot will include all post baseline data and will present ALT relative to the upper limit of normal (ULN) on the x-axis and total bilirubin relative to the ULN on the y-axis using a log scale for both axes. Reference lines for Hy's law thresholds, i.e., ALT = 3 x ULN and total bilirubin = 2 x ULN, will be added. The plot will identify group and mutational group and separate plots will be done for on-treatment and off-treatment records.

A spaghetti plot for the changes from baseline in creatine kinase (CK) over time will be presented. The actual sampling day will be used on the x-axis (baseline will be set to day 1). A solid line will be used to connect measurements; however, if the measurement was collected after the last dose of study drug plus one day, then a dotted line will be used. Group will be identified on the plot. The plot will be repeated for aldolase and troponin I. Individual CK, aldolase, ALT, AST and troponin I values relative to the ULN will be plotted over time (i.e., one plot per subject) and group and mutation type will be identified.

The actual sampling day will be used on the x-axis (baseline will be set to day 1). The day of last dose of study drug will be identified on the plot with a vertical reference line.

All individual central laboratory results will be listed. The listing will include change from baseline values and values relative to the ULN. Values outside the laboratory reference range will be identified.

Local laboratory results will not be summarized and will be listed separately from central laboratory results.

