2. INTRODUCTION

[figure not shown]
This Statistical Analysis Plan (SAP) details the statistical analyses for the REN001-202 Open Label study. REN001-202 is an open label long term (48 months) safety study in subjects with Primary Mitochondrial Myopathy (PMM) due to mitochondrial DNA mutations (mtDNA-PMM) or nuclear DNA mutations (nDNA-PMM). Subjects with mtDNA-PMM will have previously completed treatment in Study REN001-201 or participated in Study REN001-101. Subjects with nDNA-PMM who enrol in this study will be mavodelpar (REN001) naïve. As this study is an open label extension study to REN001-201 the two studies will be reported together for the REN001-202 clinical study report (CSR). Therefore, this SAP also details the planned integrated analysis for these two studies from a safety perspective and, the planned analysis will provide long term safety data of up to 54 months exposure to mavodelpar for mtDNA subjects who receive mavodelpar in REN001-201.

Figure 1 below shows the different pathways a subject can enter REN001-202 and the 5 distinct reporting groups. These groups provide the following assessments for mavodelpar 100mg once daily:

- Long-term safety data
- Long-term tolerability
- Bridging data (safety and efficacy) between nDNA-PMM subjects and mtDNA subjects

While efficacy data will be presented, these should be interpreted in a descriptive manner since the design of this open label study, does not enable obtaining either reliable or fully interpretable confirmatory evidence of efficacy, including 'durability of effect'. These limitations regarding long-term efficacy assessments are due to several key issues: the lack of a randomized comparator group, the lack of blinding when assessing effects on effort-dependent outcome measures, and the potential impact of meaningfully informative missing data.

Figure 1 Subject Reporting Groups

The data will be presented in different ways:

- from the start of REN001-202. These data presentations will focus on all 5 reporting groups and only consider data collected in REN001-202. This will allow the assessment of mtDNA-PMM and nDNA-PMM over 48 months of mavodelpar treatment. It will also provide an assessment of:
 - the continued safety of mavodelpar for subjects who received mavodelpar for 6 months in REN001-201;
 - the introduction of mavodelpar for subjects who received placebo for 6 months in REN001-201;

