3.7. ADMINISTRATION OF STUDY MEDICATION

Subjects will receive 100 mg mavodelpar orally once daily. Study drug should be taken with food at a convenient time to the subject (ideally in the morning). The exceptions to this are:

- at the Baseline visit for subjects enrolled under pathway options 2-4 ([Section 3.3](#)) the first dose will be taken with food at the site under the supervision of site staff. Subjects enrolled under pathway option 1 are expected to have taken their last dose of REN001-201 study medication that morning prior to their REN001-201 Week 24 (REN001-202 Baseline) visit, in which case their first dose of mavodelpar in REN001-202 should be taken the following day.
- at the Month 3 visit, where the subject should take the study drug at the study centre with food, when instructed to do so by the site staff.

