subjects represent. These 5 reporting groups are referenced in square brackets alongside the descriptions below. The summaries are:

- From the start of REN001-202 Summaries will be presented by mutation group (REN001 100 mg mtDNA-PMM [Groups 1 to 4] and REN001 100 mg nDNA-PMM [Group 5]). The mtDNA-PMM group will also be split by:
 - Placebo > REN001 100 mg [Group 1] – subjects who received placebo in REN001-201 and enrolled at REN001-201 W24, FU or after exit.
 - REN001 100 mg > REN001 100 mg [Group 2] – subjects who received mavodelpar in REN001-201 and enrolled at REN001-201 W24 visit.
 - REN001 100 mg >FU> REN001 100 mg [Group 3] – subjects who received mavodelpar in REN001-201 and enrolled at REN001-201 FU visit.
 - REN001 100 mg >Exit> REN001 100 mg [Groups 4a and 4b] – subjects who received mavodelpar in REN001-201 and enrolled after exiting REN001-201 or subjects who took part in REN001-101 study.

Summaries will extend out to Month 48, where applicable.

- From the start of REN001-201 which will be split by REN001-201 treatment group (REN001 100 mg [Groups 2, 3 and 4a] and placebo [Group 1]). Subjects who enrol in REN001-202 at REN001-201 Exit will only have their REN001-201 data included in these summaries. Baseline summary tables (disposition, demography, baseline characteristics, medical history and prior medications) will also include an overall summary.

Summaries will extend out to Month 54, where applicable, for all subjects who complete both studies.

- From the start of REN001 treatment [Groups 1, 2, 3 and 4]. Subjects who enrol in REN001-202 at REN001-201 Exit and receive mavodelpar in REN001-201 [Group 4a] will be counted as 2 separate subjects. Summaries will be presented over all subjects (REN001 100 mg).

Summaries will extend out to Month 54, where applicable, for subjects who receive mavodelpar in REN001-201 and enrol in REN001-202 at REN001-201 W24 or FU; for all other subjects summaries will extend to Month 48.

In addition, for summaries from the start of REN001 there is only Week 2 (Month 0.5), Week 18 (Month 4.5), Month 1 (Month 7) and Month 3 (Month 9) for subjects who receive mavodelpar in REN001-201 and therefore this visit will not be included in the by visit summaries. Refer to [Section 3.8](#) for diagram of visit assignment.

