12. ANALYSIS OF SAFETY DATA

All safety evaluations will be performed using each safety analysis set unless specified otherwise.

As the nDNA-PMM subjects will only be recruited from a subset of the REN001-202 sites, summaries may also be presented only including mtDNA-PMM subjects from the same sites. Two separate sets of subjects may be used: the subjects who received mavodelpar in REN001-201 with their data from the start of REN001-201, and the subjects who received placebo in REN001-201 from the start of REN001-202. Consideration will be given to the duration of exposure for nDNA-PMM subjects when summarising the data from the mtDNA-PMM subjects (e.g., if the duration of exposure of nDNA-PMM subjects is up to 6 months, only the first 6 months of data for the mtDNA-PMM subjects will be used).

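### The one firm direct mtDNA-versus-nDNA laboratory plot pools mtDNA subjects at different exposure stages against drug-naive nDNA subjects, so an equal drug effect can look smaller in mtDNA

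*SAP*

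**What the plan says.** SAP Section 2 lists three things that the reporting groups are meant to provide. One is "Bridging data (safety and efficacy) between nDNA-PMM subjects and mtDNA subjects".

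The display that sets the two genotypes directly against each other is in SAP 12.2. In the presentation from the start of REN001-202, "the box plot will be repeated for the overall mt-DNA-PMM versus nDNA-PMM groups". It is worded as a commitment, and it repeats box plots of change from baseline that are also planned by visit and group.

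SAP 8.2 makes the mtDNA side Groups 1 to 4 together and the nDNA side Group 5. The members differ in exposure:

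- Group 1: "subjects who received placebo in REN001-201 and enrolled at REN001-201 W24, FU or after exit". Their first mavodelpar dose is in REN001-202.
- Group 2: "subjects who received mavodelpar in REN001-201 and enrolled at REN001-201 W24 visit". SAP 3.7 adds that subjects entering by this route "are expected to have taken their last dose of REN001-201 study medication that morning prior to their REN001-201 Week 24" visit, which is also the REN001-202 baseline.
- Group 3: prior mavodelpar, entering at the REN001-201 follow-up visit after a gap of about 4 weeks (SAP 3.8).
- Group 4: prior mavodelpar, entering after a break of variable length following REN001-201 (4a), or more than 2 years after REN001-101 (4b).
- Group 5: nDNA subjects, never exposed.

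Under SAP 8.6, presentations from the start of REN001-202 use the last value before REN001-202 dosing as baseline for every group.

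SAP Sections 10 and 12 describe an mtDNA comparator aligned on exposure: former mavodelpar subjects from the start of REN001-201, and former placebo subjects from the start of REN001-202. The wording is optional: "Two separate sets of subjects may be used".

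**The concern.** Change from baseline means different things on the two sides of this plot. For nDNA subjects and Group 1 it is the change after starting mavodelpar. For Group 2 it is whatever further change occurs after about 24 weeks on drug. A shift in CK, transaminases, lipids or bone markers that has appeared by Week 24 is already in the Group 2 baseline and drops out of the plotted change.

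Pooling Group 2 with the rest pulls the mtDNA distribution towards no change. Two genotypes with the same response would then look different, with nDNA appearing the more affected. Bridging is a stated purpose, and Protocol 1.3 says the nDNA information will support further development in that population. A reader could take the difference as genetic when it comes from the choice of baseline.

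**Working it through.** The plan has no figure to reproduce. SAP 8.1 plans no testing, SAP 3.5 gives no statistical basis for the sample size, and no effect size or SD is stated. The check traces the baselines and then bounds the dilution.

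**Inputs**

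- About 150 mtDNA and up to 50 nDNA subjects (Protocol 4.5 and 8.2.2; SAP 3.5). These are enrolment estimates.
- δ: mean change from a drug-free baseline, taken as equal in both genotypes.
- f: share of mtDNA subjects with an on-drug baseline. It is not stated, and neither is the REN001-201 allocation ratio. SAP 3.8 says most subjects enter at Week 24, but that majority includes former placebo subjects. Assumed range 0.20 to 0.67, or about 30 to 100 of 150.
- k: share of the effect still to come after Week 24. Not stated; assumed 0 to 0.5.
- Groups 3 and 4 are treated as drug-free at baseline. Any residual effect in Group 3 would widen the gap.

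**Dilution**

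Pooled mtDNA mean change = δ[(1 − f) + f·k]

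Artificial gap, nDNA minus mtDNA = δ − δ[(1 − f) + f·k] = δ·f·(1 − k)

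| f | Gap, k = 0 | Gap, k = 0.5 |
|---|---|---|
| 0.20 | 0.20δ | 0.10δ |
| 0.33 | 0.33δ | 0.165δ |
| 0.50 | 0.50δ | 0.25δ |
| 0.67 | 0.67δ | 0.335δ |

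The gap vanishes at f = 0, or at k = 1 (nothing has happened by Week 24).

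**After realignment**

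With former mavodelpar subjects counted from the REN001-201 baseline and former placebo subjects from the REN001-202 baseline, f = 0 and the gap is zero under the same assumptions.

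**Precision**

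The 95% half-width for a mean difference, in SD units, is 1.96·√(1/n₁ + 1/50), where n₁ is the number of mtDNA subjects:

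- n₁ = 150: 1.96 × 0.163 = 0.32
- n₁ = 100: 1.96 × 0.173 = 0.34
- n₁ = 75: 1.96 × 0.183 = 0.36
- n₁ = 50: 1.96 × 0.200 = 0.39

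The size of Group 1 is not given; 50 to 100 is an assumed range. Even a comparison of Group 1 alone with nDNA loses little precision. The aligned set uses both former arms and would lose less.

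**The case against.** The strongest reply is that first-exposure mtDNA data are already a firm part of the plan.

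- The same box plots are planned by visit and group, and SAP 8.2 splits the mtDNA subjects into Groups 1 to 4. Group 1 and Group 5 will therefore both be shown from the REN001-202 baseline.
- SAP 8.2 applies all three approaches unless stated otherwise. The presentation from the start of REN001 treatment will therefore show former mavodelpar subjects from their pre-drug baseline.
- SAP Section 2 separates continuation, introduction and re-introduction of mavodelpar, and does not name the pooled plot as the bridging analysis.
- Nothing is tested, and no decision rule depends on this plot.

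All of this stands, and it limits the harm. It does not remove the point. SAP 8.2 confines the presentation from the start of REN001 treatment to Groups 1 to 4, so nDNA subjects are not in it, although the baseline list in 8.6 mentions them. The by-group plots require the reader to know which pair of groups to compare. The one plot that puts the genotypes head to head has the mixed baseline.

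Three stronger readings are tempting, and the documents do not support them:

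- *The plot is purely continued treatment against first exposure.* That would need f = 1. Group 1 is first exposure, and Groups 3 and 4 are re-introduction.
- *nDNA subjects would look 1.7 to 3.0 times as affected.* These ratios are 1/(1 − f) at f = 0.40 and 0.67. They need assumed shares and no further effect after Week 24. At f = 0.50 the ratio is 2.0 with k = 0, but 1/0.75 = 1.33 with k = 0.5. They are also ratios of means, whereas SAP 12.2 specifies box plots with 5th and 95th percentile whiskers and no mean. Medians and percentiles of a mixture do not scale in this way.
- *The same plot distorts early adverse events.* It shows laboratory change only.

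**Conclusion.** The point holds as one about interpretation. The only firm direct genotype plot for laboratory data mixes three exposure stages on the mtDNA side and has one on the nDNA side. For an effect that appears by Week 24, the distortion runs one way: mtDNA looks less affected.

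The range of about 0.10 to 0.67 of the true effect is illustrative. It rests on the assumed f and k, equal true effects in the two genotypes, and Groups 3 and 4 being drug-free at baseline. It describes means, so it indicates the direction and rough scale of what the box plots would show rather than their exact displacement. No primary endpoint, test or sample-size figure is affected. The change is worth making because the plan already contains the aligned comparator and leaves it optional.

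**What to change.** 1. In SAP 12.2, draw the mtDNA-versus-nDNA box plots with mtDNA subjects counted from first mavodelpar dose: former mavodelpar subjects from the REN001-201 baseline, and former placebo subjects from the REN001-202 baseline. Leave out the REN001-202 data of Group 4a and all of Group 4b, which are re-introduction.
2. In SAP Sections 10 and 12, change *may* to *will* for this exposure-aligned comparator, and keep the limit on exposure duration. Separate it from the same-site restriction, which can stay as a sensitivity display because its value depends on site overlap that is not yet known.
3. Wherever overall mtDNA appears from the start of REN001-202, label it as mixed exposure and refer the reader to the aligned display and to Group 1 against Group 5.

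The cost is SAP wording and one extra set of descriptive outputs, using baselines and visit mappings already defined in SAP 3.8 and 8.6. Routine haematology and biochemistry share Months 1, 3, 6, 12, 18 and 24 across the aligned sets. HbA1c is the exception. By SAP Appendix 2 and Protocol 6.6 and 6.9, former mavodelpar subjects have it at Months 6, 18 and 30 from first dose, and nDNA subjects at Months 12 and 24. Up to Month 24, its aligned plot would rest on former placebo subjects, and a footnote should say so.

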3.2.2 Secondary Endpoints

For mtDNA and nDNA subjects:

- Absolute values, changes from baseline, and incidence of potentially clinically significant changes in:
 - Laboratory safety tests
 - Electrocardiograms (ECG)
 - Supine vital signs
 - Eye assessments

For mtDNA subjects:

- Absolute values and changes from baseline in:

- Distance walked during the 12MWT*
- MFIS total scores and sub-scale scores*

Patient Global Impression of Severity (PGIS) scores for fatigue and muscle symptoms

- Brief pain inventory (BPI) pain severity and pain interference scores*
 - Patient Reported Outcomes Measurement Information System (PROMIS) Short Form- Functional Assessment of Chronic Illness Therapy (FACIT) Fatigue 13a scores*
 - 36-Item Short Form Health Survey (SF-36) domain scores (7-day recall)*
 - Work Productivity and Activity Impairment Questionnaire: Specific Health Problem (WPAI:SHP) scores*
 - First 6-minute walk distance and last 6-minute walk distance*
 - Phenotypic description questions*
- Patient Global Impression of Change (PGIC) scores for fatigue and muscle symptoms

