3.7.2.2 Discontinuation – All Subjects

Discontinuation or interruption of study drug should be considered, in consultation with the Medical Monitor and the Sponsor where possible, if:

- ALT or AST > 8xULN.
- ALT or AST > 5xULN for more than 2 weeks.
- ALT or AST > 3xULN and total bilirubin > 2xULN or INR >1.5.
- ALT or AST > 3xULN with the appearance of fatigue, nausea, vomiting, right upper quadrant pain or tenderness, fever, rash, and/or eosinophilia (>5%).

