3.7.3 Safety Monitoring for Kidney: Management and Stopping Rules

If subjects develop a creatinine elevation > 2xULN and more than 2x baseline value:

- Monitor creatinine 2 times per week, or as clinically indicated, until recovery.
- For subjects with > 3xULN the study drug should be withheld, and the subject should continue to be followed closely.
- In the event of either of the above continued participation in the study should be discussed with the Medical Monitor.

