8.6 Safety Analyses

No imputation will be used for handling missing data, with the exception of conservative approaches taken for missing AE information (e.g., intensity). Details of such conventions will be documented in the SAP.

Treatment-emergent adverse events will be summarized by SOC and Preferred Term, in accordance with the MedDRA coding dictionary. The number of subjects reporting each AE preferred term will be tabulated for all TEAEs and separately for those considered as at least possibly related to study treatment by the Investigator. Number of subjects reporting SAEs and AESIs will also be tabulated.

Changes from baseline in laboratory parameters (including bone and calcium markers), vital signs, ECG and eye examinations data will be summarized by visit.

The incidence of potentially clinically significant laboratory and ECG values (e.g., increase in QTcF ≥ 30 msec from baseline or an absolute QTcF value of ≥ 500 msec).

Absolute values and changes from baseline for the DXA endpoints will be summarized. Summaries will be presented over all subjects and for the following demographic sub-groups:

- Men
- Pre-menopausal women
- Post-menopausal women

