3.2.2. Secondary Endpoints

- Absolute values, changes from Baseline and incidence of potentially clinically significant changes in:

- Laboratory safety tests
- Electrocardiograms (ECGs)
- Vital signs
- Eye assessments

For mtDNA-PMM subjects

- Absolute values and changes from Baseline in:
 - Distance walked during the 12-minute walk test (12MWT)*
 - Modified Fatigue Impact Scale (MFIS) Total scores and sub-scale scores*
 - Patient Global Impression of Severity (PGIS) score for fatigue and muscle symptoms
 - Brief Pain Inventory (BPI) pain severity and pain interference scores*
 - Patient-Reported Outcomes Measurement Information System (PROMIS) Short Form – Functional Assessment of Chronic Illness Therapy (FACIT) Fatigue 13a scores*
 - 36 Item Short Form Survey (SF-36) domain scores (7-day recall)*
 - Work Productivity and Activity Impairment questionnaire: Specific Health Problem (WPAI:SHP) scores*
 - First 6-minute walk distance and last 6-minute walk distance*
 - Phenotypic description questions
- Patient Global Impression of Change (PGIC) scores (muscle and fatigue symptoms)

**Collected up to Month 24 only.*

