8.4. VISIT WINDOWS

Data will be assigned to ‘analysis’ visits using windowing (see table below). If more than one assessment (including the early termination or unscheduled assessments) falls within the same defined window, the on-treatment assessment closest to the target day with non-missing data will be used for analysis. If the scheduled visit assessment is on-treatment and within the analysis window, then this will be used irrespective of other unscheduled assessments within the analysis window. If two assessment dates are at the same distance from the target day, the latest on-treatment assessment with non-missing data will be used for analysis. Off-treatment assessments will only be assigned to a visit window in the absence of an on-treatment assessment within the analysis window.

This is the same approach as used in the REN001-201 SAP and therefore the REN001-201 data will have the same analysis visit windowing assigned as per the REN001-201 CSR.

To assess whether a REN001-202 visit is within the analysis window the day relative to the start of REN001-202 will be used. This will mean that for subjects who enrol at REN001-201 FU the interruption in study drug during the REN001-201 FU period will be ignored.

Study	Original Visit	Visit Name for Combined Study Summaries	Target Day ¹	Protocol Visit Window	Analysis Window ¹	Analysis Interval
REN001-201	Baseline	Baseline	1	NA	≤1*	NA
	Week 2	Month 0.5	14	±3	8 – 20	13 (±6)
	Week 4	Month 1	28	±3	21 – 35	15 (±7)
	Week 12	Month 3	84	±7	63 – 105	43 (±21)
	Week 18	Month 4.5	126	±7	106 – 146	41 (±20)
	Week 24	Month 6	168	±7	147 – 189	43 (±21)
REN001-202	Baseline	Month 6	1	NA	≤1*	NA
	Month 1	Month 7	28	±3	21 – 35	15 (±7)
	Month 3	Month 9	84	±7	63 – 105	43 (±21)
	Month 6	Month 12	168	±7	147 – 189	43 (±21)
	Month 9 [^]	Month 15 [^]	252	±21	211 – 293	83 (±41)
	Month 12	Month 18	336	±21	294 – 378	85 (±42)
	Month 15 [^]	Month 21 [^]	420	±21	379 – 461	83 (±41)
	Month 18	Month 24	504	±21	462 – 546	85 (±42)
	Month 24	Month 30	672	±21	630 – 714	85 (±42)
	Month 30	Month 36	840	±21	798 – 882	85 (±42)
	Month 36	Month 42	1008	±21	966 – 1050	85 (±42)
	Month 42	Month 48	1176	±21	1134 – 1218	85 (±42)
	Month 48	Month 54	1344	±21	1302 – 1386	85 (±42)

NA=not applicable.

¹ Target day and analysis windows are relative to start of each study.

* Baseline values must be prior to dosing if time of assessment is recorded.

[^] Month 9 and Month 15 (original) visits are only applicable for German sites.

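### The laboratory PCI table has no row for ALT/AST alone or for creatinine, so a secondary safety endpoint yields no subject count at the protocol's own liver-enzyme and kidney thresholds

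*SAP*

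**What the plan says.** Protocol 3.2.2 and SAP 3.2.2 both make the "incidence of potentially clinically significant changes in" laboratory safety tests a secondary endpoint, for mtDNA and nDNA subjects alike. Protocol 8.6 repeats the intention but gives only QTcF examples and no laboratory cut-off.

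The SAP supplies the definition in 12.2: "Subjects who satisfy the criteria for values of potential clinical importance (PCI), identified in the table below, will be summarized and listed". A subject is counted if any on-treatment post-baseline value, scheduled or unscheduled, meets a criterion. The rows are CK (relative to ULN or to a raised baseline), aldolase, troponin I, and potential Hy's Law (ALT or AST above 3×ULN, total bilirubin above 2×ULN and alkaline phosphatase at most 2×ULN).

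The protocol has its own numerical thresholds for the two organs concerned.

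- Liver (3.7.2 to 3.7.2.3): repeat testing when ALT or AST exceeds 3×ULN, with at least 2× baseline also required if baseline was above ULN. The discontinuation rules include ALT or AST above 8×ULN and "ALT or AST > 5xULN for more than 2 weeks". They also include above 3×ULN combined with raised bilirubin, raised INR or symptoms.
- Kidney (3.7.3 to 3.7.3.2): "If subjects develop a creatinine elevation > 2xULN and more than 2x baseline value", then further steps above 3×ULN.

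Creatinine and eGFR are in the biochemistry panel (Protocol Table 4). SAP 14 records no change from the protocol's planned analyses.

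**The concern.** The protocol treats an isolated aminotransferase rise or a creatinine rise beyond stated multiples as important enough to trigger retesting, close observation, withholding or discontinuation. The endpoint meant to report potentially important laboratory changes does not count either. The SAP gives no reason, and it is inconsistent across organs: the ECG criteria in SAP 12.5 include 500 msec for QTcF, which is also the protocol's withdrawal threshold, and CK has a baseline-adjusted row.

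At stake is whether a reader of the study report can see how many subjects crossed these lines. Long-term safety is the primary objective, and a report that follows the SAP would leave that number to be worked out from listings.

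**Working it through.** The documents state no figure on this point, so there is nothing to reproduce. The check applies the protocol thresholds and the PCI rule to the same laboratory profiles.

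**Step 1. Threshold check.** Inputs are Protocol 3.7.2 and 3.7.3 and the SAP 12.2 table. The profiles are assumed test cases: liver values are multiples of ULN, unmentioned values are normal, and liver baselines are normal.

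| Profile | Protocol threshold crossed | Counted as PCI? |
|---|---|---|
| ALT 3.5 | repeat test | no |
| ALT 6 for 3 weeks | above 5×ULN for over 2 weeks | no |
| ALT 9 | above 8×ULN | no |
| ALT 4 with symptoms | above 3×ULN with symptoms | no |
| ALT 4, INR 1.6 | above 3×ULN with INR | no |
| ALT 4, bilirubin 2.5, ALP 1.5 | above 3×ULN with bilirubin | **yes** |
| ALT 4, bilirubin 2.5, ALP 2.5 | above 3×ULN with bilirubin | no |
| Creatinine 2.5×ULN, 2.5× baseline | kidney monitoring | no |
| Creatinine 3.5×ULN, 3.5× baseline, sustained | kidney above 3×ULN | no |

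One of nine is counted. The gap is complete for ALT/AST alone and for creatinine, and partial for the combined liver threshold.

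**Step 2. Do other summaries give the count?**

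- *Shift tables (SAP 12.2)* classify values as low, normal or high. ALT at 1.2×ULN and at 9×ULN fall in the same cell.
- *By-visit statistics (SAP 8.2, 12.2)* include the maximum, so the largest windowed value at each visit is visible. They do not say how many subjects exceeded a multiple of ULN.
- *Retests.* Under SAP 8.4, if the scheduled value is on-treatment and in its window, "then this will be used irrespective of other unscheduled assessments within the analysis window". A higher retest in that window does not enter the by-visit or shift table.
- *Values between windows* are generally listed only (SAP 8.4). Leaving out the German Month 9 and 15 visits, the REN001-202 post-baseline windows cover 15 + 43 + 43 + 7×85 = 696 days. Days 2 to 1386 are 1,385 days, so 1,385 − 696 = 689 days (689/1,385 = 49.7%) lie in no summarised window.
- *German Month 9 and 15 results* are left out of by-visit summaries. SAP 6 brings them into a summary only through the PCI criteria. With no row, isolated ALT/AST and creatinine results from those visits are listed but not summarised.
- *Plots.* The eDISH plot and the individual plots show ALT against ULN, and the individual plots also show AST. Creatinine is named in none of the SAP 12.2 plots.

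**Step 3. How many subjects might this concern?** The documents give no expected rate. With the planned 150 + 50 = 200 subjects and an assumed per-subject rate p, the expected number is 200p and the chance of at least one is 1 − (1 − p)^200:

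- p = 0.5%: 1 subject, 63%
- p = 1%: 2 subjects, 87%
- p = 2%: 4 subjects, 98%
- p = 5%: 10 subjects, over 99.9%

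**The case against.** The strongest case against has four parts.

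*Much of the information is reported elsewhere.* This stands in part. All biochemistry has by-visit minimum and maximum, every central result is listed relative to ULN, and ALT above 3×ULN can be read off the eDISH plot, which uses all post-baseline data. A value the investigator judges clinically significant becomes an adverse event (Protocol 7.1.1.2, 7.1.2) and enters the AE tables. Creatinine above 3×ULN, where drug is withheld, would ordinarily qualify. But AE status rests on judgement, and Protocol 7.1.1.2 says a retest or continued monitoring is not an intervention, so the lower triggers need not appear as AEs.

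*A reader might infer that the kidney incidence will be reported as zero, that every such case goes uncounted, or that these values appear only in plots and listings.* The documents support none of these. A parameter without a row has no incidence produced, which is not a reported zero. The AE tables and by-visit statistics carry part of the information.

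*Leaving out isolated ALT/AST may be deliberate.* Protocol 3.7.1 and 3.7.2 explain that aminotransferases can rise with CK in PMM without liver disease, so requiring bilirubin as well targets liver injury. That is a fair reason for a baseline condition and a CK flag. The SAP does not state it, and it does not explain the absence of creatinine, which is the stronger half of the point.

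*The thresholds in Protocol 3.7 are management triggers, not endpoint definitions, and the study is descriptive with SRC oversight.* True. But the protocol offers no other laboratory cut-offs, and reporting counts at these levels changes no trigger.

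**Conclusion.** The point holds as a gap in endpoint definition. The PCI table produces no subject count for ALT/AST alone or for creatinine at any protocol threshold, and it counts the combined liver threshold only when alkaline phosphatase is at most 2×ULN. No other planned display gives a threshold count over all on-treatment values.

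This rests on the wording of SAP 6, 8.4 and 12.2 and on the PCI table being the only laboratory definition of the endpoint. The number of subjects affected is unknown; the range in the working depends on assumed rates. The data are not lost and the study's validity is not in question. It is a completeness correction that should be made, because safety is the primary objective and the correction costs very little.

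**What to change.** Add the following rows to the SAP 12.2 PCI table, for reporting only, under its existing rule (any on-treatment post-baseline value, including unscheduled):

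- ALT or AST above 3×ULN, and at least 2× baseline if baseline is above ULN
- ALT or AST above 5×ULN, optionally flagging more than 2 weeks' duration
- ALT or AST above 8×ULN
- creatinine above 2×ULN and above 2× baseline
- creatinine above 3×ULN

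The 5× and 8× rows should carry no baseline condition, because Protocol 3.7.2.2 has none. For example, a baseline of 4.5×ULN rising to 8.5×ULN is 8.5/4.5 = 1.9 times baseline. It crosses the protocol's 8×ULN rule but would be dropped if a doubling of baseline were required.

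Beside the ALT/AST rows, note that such rises may accompany CK elevation in PMM, for example by flagging concurrent CK. If the sponsor prefers to leave any row out, the SAP should say why.

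The cost is a few extra rows from data already collected. The downside is that some muscle-origin ALT/AST rises will be counted, which the CK flag makes visible. Two limits remain: local laboratory results are not summarised under SAP 12.2, so a peak measured only locally would still be missed, and the rules that add INR or symptoms need data beyond the Table 4 panel. No threshold or action for managing subjects is altered.
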